4.2 Pre-Treatment Session

Although the intervention components will all be delivered remotely, we will have one in-person, pretreatment training meeting with participants in order to complete screening and ensure measurement accuracy. A) Technology. Participants will have the Opt-IN app installed on their Smartphone. The program connects to a cloud server that organizes participant's time-stamped eating and activity data and transmits it to a study coach. B) Randomization. Participants will be notified of which condition they are randomized to. D) Training. After installing the app and learning which condition they have been randomized to, staff will provide instruction on how to locate and enter foods from the CalorieKing nutrient database of >50,000 foods that is resident on the server (with back-up copy on the Smartphone). Participants will learn how to interpret traffic light-colored icons that depict calorie and fat intake relative to goals. They will be taught to enter physical activity. They will also be trained, using food models, and tested on how to accurately estimate and record portion sizes, condiments, and food preparation methods. Participants in all conditions will be asked to enter their dietary intake, physical activity, and weight into the Smartphone daily throughout the day for the duration of the study. Time stamped data from the Smartphone will upload automatically to the study server throughout the day, where it will be visible to the coach. Over a 6-month period, the coach will provide either 12 or 24 sessions of telephone coaching, motivational support, and problem solving about diet, activity, and self-regulation based upon web based lessons and the participant's self-monitoring data.

4.2.1 Screening Tools

Standardized screening questionnaires will ask about demographics, anthropometrics, motivational readiness to change, physical activity readiness, and scheduling availability. The Physical Activity Readiness Questionnaire (PAR-Q) (Thomas et al., 1992), designed for adults aged 15-69, asks about 7 physical risk factors (e.g., chest pain, dizziness, joint problems). Participants who report any one factor are asked to obtain their physician's approval to enroll in Opt-IN. To screen out pre-contemplators whose low motivation to change would likely impede their success in the trial, we will use Logue's Readiness to Adopt Weight Control Behaviors scale to assess motivational readiness to change. The scale assesses readiness to change physical activity (Sutton et al., 2003). The PRIME-MD and PHQ (Spitzer et al., 1999) will be administered to screen out candidates whose suicidality or bulimia could place them at risk in a weight loss trial, or whose uncontrolled substance abuse or binge eating disorder could interfere with program adherence. Candidates for this trial will be screened for substance abuse/dependence to identify those who have substantial substance abuse issues that could interfere with program adherence,

as well as identifies severe risk behaviors related to substance abuse that would be best addressed before those that we are targeting. Similarly, study candidates who screen positive for either Bulimia Nervosa or Binge Eating Disorder (PRIME-MD) or Major Depressive Disorder (PHQ-9) would benefit from more intensive care than the targeted behavior change that is addressed in this trial. Enrolling those who have any of these conditions would put them at more risk than what is admissible to protect research subjects. Prior to the screening, participants will be notified that all information will be kept confidential, with the exception of the limits of confidentiality by mandated reporters who are required to report suspected abuse, neglect or clear intention to do harm to themselves or anybody else. In the incidence that participants do indicate substance abuse/dependence, Bulimia Nervosa, or Binge Eating Disorder, they will be given referrals to local professionals and human service agencies. If participants indicate, or the screener assesses that they are in need of emergency services, they will be escorted to the emergency room at Northwestern University, where they will be assessed and given the opportunity to deny further care. A list of local referrals and alcohol and substance abuse services are located in the Appendix.

4.2.2 Primary Outcome: Weight

Weight will be measured at baseline, 3, and 6 months. Measurements will be taken without shoes, wearing light clothing on a calibrated beam balance scale. Height will also be measured using a stadiometer, and Body Mass Index (BMI) will be calculated as weight in pounds/(height in inches)²) x 704.5. Waist circumference, a predictor of abdominal visceral fat also will be assessed. Measurement will be done twice during expiration, taking the average for analyses, by positioning an anthropometric tape midway between the palpated iliac crest and the palpated lowest rib margin in the mid-axillary lines. If participants are unable to attend in-person assessments, a self-reported weight will be obtained from the participant (see Appendix).

Participants will also complete an Exit Interview at the 6-month assessment assessing general feedback about the study, as well as any potential confounding variables. Specifically, the Exit Interview will examine intervention component preference, social support (both with the coach and other participants/buddies), and participation in other weight loss programs.

Table 5: Assessment Schedule

	Measure	Screening	Baseline	3 months	6 months
Primary Outcome	Anthropometric Measures (Weight, Waist Circumference)	X	X	X	X
Hypothesized Mediators	Adherence (call session participation; diet, activity, & weight self-monitoring)		X	X	X
Exploratory Mediators	Self-Efficacy		X	X	X
	Self-Regulation		X	X	X
	Supportive Accountability		X	X	X
	Facilitation		X	X	X
Exploratory Moderators	Demographics	X			
Exploratory Confounding Variables	Intervention component preference, social support (with coach and other participants/buddies), and participation in other programs				X

Screeners	Logue's Readiness to Adopt Weight Control Behaviors scale	x			
	PRIME-MD	x			
	PAR-Q	x			

4.2.3 Mediators

A. Hypothesized Mediator: Adherence. 1. Treatment Adherence will be operationalized as the number of treatment sessions completed, divided by the number of treatment sessions offered (12 or 24). Make-up sessions completed within a week of the target date will count as attended. 2. Self-Monitoring Adherence will be operationalized as the number of days of recording: a) weight; b) dietary intake (totaling at least 1000 kcal); c. physical Activity operationalized as the number of days of recording physical activity.

B. Exploratory Mediators. 1. Self-Efficacy. Self-efficacy will be assessed to examine treatment effects on confidence about performing two categories of behaviors associated with weight loss: diet (Stich et al., 2009) and physical activity (Marcus et al., 1992). The Scenario-Based Dieting Self-Efficacy Scale (DIET-SE) is 11 items long, and there are three subscales: High-Caloric Food (HCF; 4 items), Social and Internal Factors (SIF, 4 items), and Negative Emotional Events (NEE; 3 items). The internal consistency of the DIET-SE is good ($\alpha = .77$ for HCF; $\alpha = .79$, 4 items; and $\alpha = .79$ for NEE; total score $\alpha = .87$). Test-retest correlations for a 2- to 3-week interval were $r = .83$ for the DIET-SE scale, $r = .75$ for the HCF, $r = .77$ for the SIF, and $r = .80$ for the NEE subscale, indicating high test-retest reliability. The Self-Efficacy of Exercise Behavior Change measure includes 18 items. The scales are 13 and 18 items long, respectively. Participants use a 5-point Likert scale (1 = not at all confident; 5 = completely confident) to rate how confident they are that they will be able to eat healthy/exercise when “other things get in the way” such as being depressed, anxious, busy, or being tired. 2. Self-Regulation. Self-Regulation will be assessed by the Restraint and Disinhibition subscales of the *Three Factor Eating Questionnaire (TFEQ)* (Stunkard & Messick, 1985). Autonomous versus Controlled Motivation for Self-Regulation will be assessed using both subscales of the 15-item *Treatment Self-Regulation Questionnaire (TSRQ)*. The TSRQ shows evidence of acceptable reliability and validity; (Cronbach's α ; Controlled Motivation = .79; Autonomous Motivation = .58) (Williams et al., 1996). 3. Supportive Accountability. This exploratory mediator will be measured by assessing two constructs that define supportive accountability: therapeutic alliance and perceived autonomy support. Therapeutic alliance will be measured by the *Combined Alliance Short Form- Patient Version (CASF-P)* (Hatcher & Barends, 1996), a 20-item measure with Cronbach's $\alpha = .93$. Perceived autonomy support will be measured by an adapted version of the *Perceived Autonomy Support Scale for Exercise Settings (PASSES)*; $\alpha = .92$ (Hagger et al., 2007). 4. Facilitation. Facilitation will be measured by having participants use a 5-point Likert scale (1 = not at all; 5 = very much) to rate how much the tools provided by the study have changed their environment to make it easier to: “eat healthier,” “be more physically active,” and “lose weight.” We will also assess facilitation via the 26-item *Weight Management Support Inventory (WMSI)* (Rieder & Ruderman, 2007) which assesses the degree to which the social environment discourages excess eating and encourage exercise ($\alpha = .90$, test-retest reliability = .75, $p < .001$.)

4.3 Study Procedures

The goal of the proposed study is to determine the optimal composition of a technology supported intervention for obesity that minimizes expense and burden to participants, while achieving 6 month weight loss outcomes comparable or superior to those achieved by the current full cost, full burden form of INLIs (DPP, 2002; Look AHEAD, 2007). All intervention components to be examined were selected based on the Opt-IN model's prediction that they enhance behavioral adherence to weight regulation via the designated pathways. Additionally, all

components meet two criteria: (i) that their relative advantage in terms of influence on weight loss is currently unknown, and (ii) that their relative advantage in terms of cost and/or burden is clear. Components and their mechanisms are outlined in Table 1; the rationale for each component follows.

4.3.1 Intervention Component Selection

The CORE will be delivered to all participants to build essential competencies needed for weight loss. The CORE conveys knowledge about energy balance and the energy contribution of different foods and activities. It also includes training in how to set intake/ expenditure goals and how to conform behavioral choices to goals. The CORE will be conveyed via internet lessons, telephone coaching, and provision of a tool that reinforces participants for making healthy choices in their own environment. The tool, an application installed on participant's Smartphone, prompts real time tracking of diet and physical activity, with data uploaded to a coach who fosters accountability.

1. Telephone Coaching Intensity. A greater number of treatment sessions is well-established to result in greater weight loss (NHLBI, 1998; Wadden et al., 2005), but more sessions are also more costly and more burdensome to participants and providers. The original DPP and Look AHEAD INLIs included 16 and 36 core sessions, respectively; current standard of care for behavioral weight loss is 24 sessions (Thomas et al., 1992). Others have shortened obesity treatment to fewer than 16 sessions, with variable results (Davis-Smith et al., 2007; Martin et al., 2008; Whittemore, 2011; Whittemore et al., 2009), and with the general finding that achieving weight loss comparable to longer treatment requires adding supplemental intervention (Whittemore, 2011; Whittemore et al., 2009). We expect the supplemental treatment components tested in Opt-IN to bolster the impact of the lower intensity 12 session treatment. Since paying for the time of trained interventionists is usually the greatest cost of an INLI, a 12 session INLI with supplemental components that make its yield equivalent to a treatment twice its length would represent a very substantial advance in scalability.

2. Report to Primary Care Provider (PCP). Except when medication or food provision has been part of treatment, weight loss treatment offered by providers in the primary care setting has yielded disappointing results (Tsai & Wadden, 2009; Martin et al., 2008; Christian et al., 2008; Wadden et al., 2011). Nevertheless, patients want and expect their PCP to support their weight management (Potter et al., 2001). Reporting the patient's weight loss progress to their PCP for discussion during regular check-ups was part of Appel et al's (2011) successful bundled treatment. Although the impact of PCP reporting on its own currently cannot be disentangled, providing a report that engages the PCP to endorse the patient's weight loss is certainly less costly and more scalable than requiring the PCP to directly provide weight loss treatment. We posit that informing patients that their progress is being reported to the PCP supports weight loss efforts by supportive accountability: creating the perception that the health care team is "looped in" and paying attention, encouraging the patient to feel supported and held accountable.

3. Text Messages. Text messaging shows promise as a cost-effective channel to prompt health behavior change (Free et al., 2011; Patrick et al., 2009; Haapala et al., 2009). We are using texts in ENGAGED, as we previously used e-mails in MBC, to sustain motivation and connection in between coaching contacts.

4. Meal Replacements. The use of meal replacements to foster weight loss has a strong evidence base (Heymsfield et al., 2003; Noakes et al., 2004; Wadden et al., 2011; [name] et al., 2004). However, most trials, including our own, have provided the food products free of charge

(Goodpaster et al., 2010; Wadden et al., 2011; Look AHEAD, 2007). We judge that providing many months of free food is an unsustainable strategy for most treatment contexts, and will therefore test a more scalable real world version. Those Opt-IN participants randomized to the active arm of the meal replacement treatment component will be advised to use meal replacement products as part of their approach to controlling dietary intake. Slimfast products, as tested in Look AHEAD and widely available in grocery stores, or similar meal replacements will be recommended as offering a low-cost way to achieve calorie control. Participants randomized to active meal replacement will also be provided with one week's supply of meal replacements (e.g., 2 shakes and 2 bars per day), as an initial introduction.

5. Buddy Training. Social support is a well-documented correlate of successful health behavior change, prompting numerous efforts to harness peers as treatment agents. Engaging peers together in treatment groups has augmented weight loss (Wadden et al., 2011), and training peers to be supportive has yielded varying degrees of improved health behavior change (Gruder et al., 1993; Hogan et al., 2002; May & West, 2000; Katula et al., 2011). While we find it unrealistic to expect all individuals to have a buddy able to attend in-person groups, pilot data from ENGAGED indicate that 100% of participants can identify a support person from either their local or virtual environment. All buddies will first receive a document with information on how to provide support for his/her friend or family member after consenting to participate. The chosen support person for those randomized to receive buddy training will be coached further on how to provide support for his/her friend. Training will occur via one individual telephone coaching session, followed by four online webinar lessons on empathy, facilitation, problem solving, and behavior change skill training. Each webinar will last approximately 30-45 minutes. These trainings will be delivered quarterly, and content will be adapted from existing curricula (Nettles & Belton, 2010; West et al., 1998). Each webinar will comprise didactics followed by a group supervision for buddies. Supervision will involve shared problem solving about challenges in supporting participants. Buddies who are randomized to a condition requiring training and webinar participation will receive a \$5 online gift card after attending each required webinar, and will have the opportunity to receive a \$20 gift card bonus if they attend 3 or 4 of the 4 required webinars.

4.3.2 Intervention Component Cost Estimation

Table 2 shows the estimated cost of implementing the CORE, plus the cost of the low and high

Table 2- Estimated Cost of Lowest vs. Highest Level of Intervention Components		
Intervention Component Levels	Cost/person Lowest Level	Cost/person Highest Level
1. Phone Sessions: 12 or 24	\$86.52	\$173.04
2. PCP: no reports or reports	\$0	\$34.88
3. Texts: no or yes	\$0	\$0
4. Meal Replacements: no or yes	\$0	\$29.96
5. Buddy Training: no or yes	\$0	\$68.82
+. Core intervention cost	\$281.67	\$281.67
	Minimum cost \$ 368.19	Maximum cost \$588.37

levels of each supplemental intervention component. The CORE infrastructure that makes the intervention accessible to all participants involves a: (a) web portal on a server; (b) Smartphone application. The web portal will house a series of interactive lessons that can be assigned as 24 single lessons or as 12 pairs. The portal also receives weight, diet, and physical activity data transmitted by the patient. Uploaded data and information about lesson access and completion

are conveyed to coaches via a web interface. The Opt-IN Smartphone application, originally developed for ENGAGED, transmits dietary intake and physical activity data to the portal. To estimate the cost of implementing the intervention, we assume that all components of the system are fully developed. Two main implementation costs remain: 1) \$70 annual fee to access the study's web infrastructure, including the CalorieKing food database, interactive lessons, and coach interface; 2) technical support, estimated at 20% effort for a technician with an annual salary of approximately \$65k/year. We estimate the cost of maintenance per person to be $(\$65k * .20 \text{ effort}) / 150 \text{ participants/year} = \$86.67/\text{person}$. Thus, the total cost of the CORE is $\$70 + \$125 + \$86.67 = \$281.67/\text{person}$.

(1) Telephone Coaching session cost was estimated assuming that a health educator salaried at \$30,000 year (\$14.42/hour) offered 12 [$14.42 * 0.5 * 12 = \$86.52/\text{person}$] or 24 [$14.42 * 0.5 * 24 = \$173.04/\text{person}$] sessions (up to 20 minutes of phone coaching, plus 5-minutes to prep for the call by reviewing notes, plus 5 minutes to record notes after the call). (2) PCP Reports. Half of the participants will have two reports of their weight loss progress sent to their PCP (at 3-months, and 6-months), as per Appel et al. (2011). Direct costs of sending these reports is for staff salary to generate and print reports and cover letters and obtain signatures ($\$30 \times 1 = \$30/\text{person}$), and for postage stamps ($\$0.44 \times 2 = \$0.88/\text{person}$). Indirect costs will cover the printing and stationary ($\$2 \times 2 = \$4/\text{person}$). Total cost: $\$34.88/\text{person}$. (3) Text Messaging. That half of the sample randomized to text messaging will receive automated texts seven times per week. Text messages will be sent from a computer terminal that permits us to send texts for free through the Opt-IN application. (4) Meal Replacement. Those recommended to use meal replacement products will be given a one-week supply of Slim Fast or similar meal replacement product (14 shakes and 14 bars). $14 \text{ shakes} * \$1.35/\text{shake} + 14 * \$0.79/\text{bar} = \$29.96/\text{person}$. (5) Buddy Training. Project staff will perform the training. After an initial individual telephone training for those randomized into a Buddy Training condition, further training and supervision will occur via group phone calls/webinars. Every six weeks, study coordinators will offer the training at a variety of times/dates. Four different webinar topics will be offered to accommodate new buddies just joining the trial. Estimated staffing cost per person for this training is $\$28.82/\text{person}$: 45 minutes for initial training + 1.25 hours for 3 shared 1-hour group teleconferences). Buddies randomized to receive additional training and webinars will receive \$5 online gift cards after completion of each webinar, and an additional \$20 online gift card for completing at least 3 of the 4 webinars. Total cost of buddy training is $\$68.82/\text{person}$.

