1.2 Study Objective

The overall objective of the proposed research is to use an innovative methodological framework, the Multiphase Optimization Strategy (MOST) ([name] et al., 2007), to design, for the first time, an optimized, scalable version of a technology-supported INLI for obesity. MOST involves highly efficient randomized experimentation to assess the effects of individual treatment components, and thereby identify which components and component levels make important contributions to the overall program effect on weight loss. This information then guides assembly of an optimized treatment package that achieves target outcomes with least resource consumption and participant burden. Because the intervention strategies being tested minimize in-person coaching and leverage technology that participants already own, the new optimized intervention, to be called Opt-IN, will be more scalable than traditional INLIs. Opt-IN will thus enjoy greatly increased reach, and enable significant progress in the fight against obesity.

1.3 Primary Aim 1

To identify which components/component levels from five components under consideration for inclusion in Opt-IN contribute meaningfully to improvement in (a) average weight loss, and (b) percent achieving >7% weight loss among obese adults over a 6-month period. The five components to be tested will be: (1) coaching intensity (12 vs. 24 phone sessions), (2) text messaging (No vs. Yes), (3) progress report to participant's primary care provider (No vs. Yes), (4) recommendation to use meal replacements (No vs. Yes), (5) training participants' self-selected buddies to be supportive (No vs. Yes). We will use a highly efficient experimental strategy powered to detect effects of individual components as well as all two-way interactions.

1.4 Primary Aim 2

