To apply the results obtained in Primary Aim 1 to build (1) an intervention made up of only active components and (2) if necessary, a second intervention that is optimized for scalability. Intervention (1) will be made up of the best set of components and component levels, based on the results of the experiment conducted in Primary Aim 1. Our conversations with private insurers suggest that in order to be scalable, Opt-IN needs to be implementable for \$500 or less. If Intervention (1) exceeds an estimated cost of \$500, we will identify the combination of components and component levels corresponding to the largest treatment effect that can be obtained for implementation costs of \$500 or less. This will be the new Opt-IN intervention.

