3.3.2 Inclusion Criteria

Eligibility Criteria. Enrollees will be adults between ages 18 and 60 with BMI 25-40. At least half will be female; half will be ≥ 45 years of age. They must be weight stable (no loss or gain ≥ 25 lbs for the past 6 months), not enrolled in any formal weight loss program or taking anti-obesity medications, but interested in losing weight. Candidates must own a Smartphone (Android or iOS) and be willing to install our Opt-IN app so that their data can be transmitted wirelessly to a study coach. They must be able to use the app to record dietary intake, physical activity, and weight onto the Smartphone. Prior to participating in any study procedure, they must voluntarily

provide informed consent. “Buddy” participants must be at least 18 years old, have access to a computer and internet, be willing to undergo “Buddy Training” and participate in 4 webinars, and be willing to provide support and encouragement to the participant.

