Primary Aim 2 is to make decisions about intervention components and component levels based on the factorial experiment results. We propose to use a modified version of a decision making approach frequently used in engineering (Wu & Hamada, 2000), which emphasizes main effects, using interactions as additional valuable information. This emphasis is consistent with our objective of identifying a set of components and component levels in which each component is making a detectable contribution to the overall effect, and any inactive components have been eliminated. We remind the reader that the mixed model analysis will be performed using effect coding, which will keep any covariances among main effects and interactions to a minimum. This makes it reasonable to start the decision making process by examining main effects, and then to consider interactions carefully in subsequent steps in the process. (Recall that our theoretical model does not predict any substantially-sized higher-order interactions, which is the basis for selection of the highly economical fractional factorial design. This Resolution V design enables examination of all two-way interactions.) The decision making process can be summarized as follows: Step 1: Initial tentative selection of components and component levels, consisting of identification of the components that show a significant main effect on the primary outcome variable, weight. If buddy training, recommended meal replacements, texting, or PCP report have a significant main effect, they will tentatively be selected for inclusion in the intervention. If there is a significant positive main effect of Number of Phone Coaching sessions, this is evidence that the more expensive level (24 sessions) performs better than the less expensive level (12 sessions), so it should be selected; otherwise, the less expensive level should be selected. Step 2: Consideration of interactions and final decision. Next we will examine interactions to look for any indication that we should consider reversing a decision made in Step 1. For example, suppose both Texting and PCP Report have significant main effects, so they were tentatively selected in Step 1. If there is a significant negative interaction between them, this means that the combined effect of Texting and PCP Report is less than the sum of the main effects. Suppose Texting has the larger main effect of the two. In that case we will start from the premise that Texting is selected, and then pose this question: When Texting is selected, *does PCP Report have a large enough incremental effect to justify its selection?* This question can be addressed by examining the simple effect of PCP Report when Texting is at the Yes level. Similar decision making logic will be used to examine all significant interactions that involve any components selected in Step 1 to arrive at the final decisions about selection of components and component levels. Step 3: Identifying the combination of components and levels that produces the largest effect that can be obtained for \$500 or less. If the costs associated with the combination of component and component levels selected in the process described above exceeds the upper limit of \$500, it will be necessary to consider less expensive versions of the intervention. Using as a starting point the set of components and component levels selected in Step 2, we will examine various scenarios in which we remove Yes/No components and change the levels of Either/Or components, and compute the expected outcome based on the regression parameters obtained in the statistical analysis to select the one with the largest expected effect that can be delivered for under \$500.

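### The CORE cost lists two items worth $156.67 but is totalled at $281.67 with an unnamed $125, and that term decides whether the $500 ceiling can ever bind

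*Combined protocol and SAP*

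**What the plan says.** Section 4.3.2 costs the CORE for implementation after the trial. It states that "we assume that all components of the system are fully developed" and then that "Two main implementation costs remain". Two numbered items follow:

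- $70, described as the "annual fee to access the study's web infrastructure, including the CalorieKing food database, interactive lessons, and coach interface";
- technical support, at 20% of a salary of about $65,000 spread over 150 participants a year, or $86.67 per person.

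The concluding sentence totals the CORE as $70 + $125 + $86.67 = $281.67 per person. Table 2 enters $281.67 in both its lowest-level and highest-level columns and reports a minimum of $368.19 and a maximum of $588.37.

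The figure feeds a decision rule. Section 1.4 (Primary Aim 2) begins the rule with "If Intervention (1) exceeds an estimated cost of" $500; in that case the strongest combination costing $500 or less becomes Opt-IN. Step 3 in Section 5 applies the rule by dropping components or lowering levels, so as to "select the one with the largest expected effect that can be delivered for under" $500.

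**The concern.** The total does not follow from the items listed before it. The sentence is worded as a conclusion from two costs, yet it contains three terms, and the unexplained one is the largest. Every non-zero supplement in the same section is itemised, down to postage stamps.

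The surrounding text does not supply the missing item. Development cost is excluded by assumption. Section 1.2 says the strategies under test "leverage technology that participants already own", and Section 3.3.2 makes owning a smartphone an entry requirement, so buying a phone is not an obvious candidate.

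What is at stake is the content of the final intervention. If the $125 is not a real cost, Step 3 could remove an active component, or halve the coaching calls, to meet a ceiling that the package did not breach. If it is real and someone deleted it as a slip, every package would be understated by $125. If the question is left open until the effects are known, keeping or dropping the term could in practice choose the package.

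**Working it through.** **Inputs** (Section 4.3.2 and Table 2, per person): calls $86.52 (12) or $173.04 (24); PCP reports $34.88; texts $0; meal replacements $29.96; buddy training $68.82. Ceiling $500 (Section 1.4; Section 5, Step 3).

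**Step 1: reproduce the plan's figures.**
- Technical support: 65,000 × 0.20 / 150 = 86.67.
- CORE: 70 + 125 + 86.67 = 281.67.
- Minimum: 281.67 + 86.52 = 368.19.
- Maximum: 281.67 + 173.04 + 34.88 + 0 + 29.96 + 68.82 = 588.37.

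All agree with the plan.

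**Step 2: CORE from the two named items.** 70 + 86.67 = 156.67. The unnamed share of the stated CORE is 125 / 281.67 = 44%.

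**Step 3: cost all 32 combinations both ways.** Texting is free, so each profile below stands for two combinations. These are all the profiles that exceed $500 with the $125.

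| Profile | With $125 | Without |
|---|---|---|
| 12 calls + PCP + meal + buddy | 501.85 | 376.85 |
| 24 calls + PCP + meal | 519.55 | 394.55 |
| 24 calls + buddy | 523.53 | 398.53 |
| 24 calls + meal + buddy | 553.49 | 428.49 |
| 24 calls + PCP + buddy | 558.41 | 433.41 |
| 24 calls + PCP + meal + buddy | 588.37 | 463.37 |

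With the term, 6 × 2 = 12 of 32 exceed $500. Without it, 0 of 32 do, and the range is 156.67 + 86.52 = 243.19 to 463.37. No combination costs exactly $500, so it makes no difference that Aim 2 allows $500 or less while Step 3 asks for under $500.

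**Step 4: break-even values for a third CORE item.**
- Any package can exceed $500 only if the item is more than 500 − 463.37 = $36.63.
- The 12-call package with every supplement is excluded only if the item is more than 500 − 376.85 = $123.15. At $125 it is out by $1.85.

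**Step 5: sensitivity to call length.** Section 4.3.2 prices each call at 30 minutes (up to 20 on the phone, 10 for preparation and notes), whereas Section 4.4 describes calls of about 10–15 minutes. At 15 + 10 = 25 minutes, 12 calls cost 14.42 × 25/60 × 12 = $72.10 and 24 cost $144.20.
- With the $125, the first three profiles fall to 487.43, 490.71 and 494.69. The other three stay above the ceiling (524.65, 529.57, 559.53), so 6 of 32 exceed $500.
- Without the $125, the maximum is 463.37 − 28.84 = 434.53 and none does.

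**The case against.** Four points can be made for the plan.

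- **The sums are correct.** This is true. The fault is an input with no description, not an error of addition.
- **The text speaks of main costs, so smaller ones may be unlisted.** The list is not literally exhaustive, but this reading cannot account for the largest of the three terms.
- **A lost description is plausible.** The $281.67 is used consistently in the sum and throughout Table 2. The CORE is said to have two parts, a web portal and a smartphone application. The $70 covers web access, and no item is labelled as an application cost. Phone ownership rules out buying phones, not other delivery costs, and assuming a finished system rules out development cost, not running cost. This stands as a reason not to treat the $125 as a mistake. It does not identify the cost, and a real cost would still need to be named.
- **The counts are more exact than the inputs, and the consequence is conditional.** Both parts stand. The 12 of 32 and the $1.85 margin hold at Table 2 prices only; with 25-minute calls the count is 6 and the $1.85 exclusion disappears. Step 3 is reached only if Steps 1 and 2 select a package above the ceiling, and 20 of 32 are below it even with the $125. The contrast between some packages and none survives the change in call length.

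Nor does the extraction of the text explain the gap. The $125 sits inside an intact equation with no sign of redaction, and the appendix list shows no costing appendix.

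**Conclusion.** The concern holds. The stated CORE cost of $281.67 does not follow from the two items given for it, which sum to $156.67; the $125 difference has no stated source. At Table 2 prices this term moves the number of combinations above $500 from 0 to 12 of 32, so it determines whether the cost rule of Primary Aim 2 can bind.

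The conclusion rests on the other Table 2 prices being as stated and on the $125 not being described in material that was unavailable. It does not rest on the $125 being wrong, which the documents do not settle. Whether the ceiling does bind depends on which components are selected. This should be fixed, but it does not threaten the trial's validity: the Aim 1 estimates and the power calculation do not use the figure.

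**What to change.** Reconcile the CORE sum with its list, ideally before component effects are estimated, so that the cost input is not settled once the active components are known. There are two routes:

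- **If the $125 is a real cost,** name it as a third item, give its per-person basis for the intervention as now delivered, and keep $281.67 and Table 2.
- **If it is not,** remove it and restate the CORE as $156.67, with a Table 2 minimum of $243.19 and maximum of $463.37.

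Then rerun the $500 screen over all 32 combinations. If the item cannot be sourced, report the Step 3 choice both with and without it. While the section is open, the call length used for costing should be reconciled with the one in Section 4.4, because it also moves packages across the ceiling.

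The cost is one sentence and one table. Participants, randomisation, data collection, power and the Aim 1 analysis are not touched.
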